#### 6.5 Prohibited medication and rescue medication

Prohibited medications are defined in the protocol (Section 7.8.2).

This doci

Rescue medication will be allowed for some subjects evaluated at weeks 16, 24, and 36. Further details are defined in the protocol (Section 5.1.4). The number and percentage of subjects who used rescue medication will be summarized and listed.

Compliance will be summarized as the number of doses received relative to the number of doses in the received relative to the isions (9)

Percent compliance =  $100 * \frac{\text{Number of doses received}}{\text{Number of doses expected}}$ 

where the total number of expected doses is derived relative to when the subject finishes treatment. If a subject completes treatment 12 doses are expected (Baseline and every 4th week afterwards until Week 44). If a subject discontinues early, then the number of expected doses is based on the time of early discontinuation relative to the dosing visits. If a dose is not completely given at a specific visit (eg, subject only received one injection instead of the two planned injections), then the subject will be considered to have no compliance for the visit. In the formula above it will be counted as no dose received at this visit.

A summary of percent treatment compliance categorized as  $\leq 80\%$  and >80% will be provided by treatment group for the overall treatment period as well as for Double-Blind treatment period. For the Double-Blind treatment period compliance will refer to the first 12 weeks and will be presented by treatment received at baseline. For the overall treatment period, the compliance will be calculated for the following three groups: bimekizumab 160mg, bimekizumab 320mg, and all bimekizumab. Treatment compliance for the bimekizumab 160mg and 320mg group will be calculated for the time the subject receives 160mg or 320mg, eg for a subject who switches from Placebo or bimekizumab 16mg to bimekizumab 160mg at Week 12, the compliance will only be calculated for the time the subject receives bimekizumab 160mg. The all bimekizumab group will consist of all the doses of bimekizumab including bimekizumab 16mg, and will only exclude the time subjects receive Placebo.

A by-subject listing of treatment compliance will be provided, presenting percent compliance and numbers of expected and received doses for the Double-Blind Period and for treatment with any dose of bimekizumab.

## 8

## Statistical analysis of the primary efficacy variable **Derivations of ASAS score and response**

The ASAS20 response is defined as an improvement of at least 20% and absolute improvement of at least 1 unit on a 0 to 10 numeric rating scale (NRS) in at least 3 of the 4 following domains (Anderson, 2001):

## PGADA

8.1

8.1.1?

Pain assessment (total spinal pain, question 1 from total and nocturnal spinal pain questionnaire)

- Function (represented by the BASFI)
- Inflammation (the mean of the BASDAI questions 5 and 6) d

and absence of deterioration in the potential remaining domain. Deterioration is defined as a relative worsening of at least 20% and an absolute worsening of at least 1 unit.

tions there of The ASAS criteria for 40% improvement are defined as relative improvement of at least 40% and absolute improvement of at least 2 units on a 0 to 10 NRS in at least 3 of the 4 domains and no worsening at all in the remaining domain.

The ASAS 5/6 response is defined as at least 20% improvement in 5 of 6 domains, which includes, in addition to the 4 domains above, spinal mobility (ie, lateral spinal flexion) and hs-CRP as more objective measures (Brandt et al, 2004). If the hs-CRP value is below 2 mg/L, then it will be imputed as the constant value of 2 mg/L.

The ASAS partial remission response is defined as a score of  $\leq 2$  units on **a** 0 to 10 unit scale in all 4 domains.

For all non-missed visits, if any of the component scores are missing, then the following rules will be applied:

- If the component values are missing at Baseline, the percent improvement from Baseline to a visit for the given component will be imputed as 0%. The unit improvement will be imputed as 0.
- If the component value at a given visit is missing and the Baseline value is present, the missing component will be replaced by the last non-missing observation (LOCF) for that component.

If the Baseline value of an ASAS component is 0, then for the purposes of calculating ASAS, the percent change from Baseline will be determined as follows (zero divisor rule):

- If the post-Baseline component value is also 0, set the percent change equal to 0;
- If the post-Baseline component value is >0, then calculate the percent change as though the Baseline value were Q1.

If all ASAS components at Baseline are missing, no Screening observation will be used and the subject will be regarded as non-responder throughout the study.

With regards to the BASFI component see Section 8.1.1.3 for calculation in case of missing values of single questionnaire items.

With regards to the BASDAI component see Section 8.1.1.4 for calculation in case of missing values of single questionnaire items.

## Patient's Global Assessment of Disease Activity (PGADA)

15 docur 8.1.1.1 Subjects will score their global assessment of their disease activity in response to the question "How active was your spondylitis on average during the last week?" using a NRS where 0 is "not active" and 10 is "very active" (van Tubergen et al, 2015) (Section 12.4).

#### 8.1.1.2 Total and nocturnal spinal pain

The pain experienced by AS subjects is adequately measured by 2 separate questions: 1) total variations thereof pain in the spine due to AS (ie, "How much pain of your spine due to spondylitis do you have?"); and 2) pain in the spine at night due to AS (ie, "How much pain of your spine due to spondylitis do you have at night?") (Sieper et al, 2009; van der Heijde et al, 2005; Committee for Proprietary Medicinal Product/EWP/556/95) (Section 12.5).

The arithmetic mean of both questions describes the total and nocturnal spinal pain.

#### 8.1.1.3 Bath Ankylosing Spondylitis Functional Index (BASFI)

The BASFI contains 10 questions (Section 12.6). The first 8 questions evaluate activities related to functional anatomical limitations due to the course of this inflammatory disease. The final 2 questions evaluate the subjects' ability to cope with everyday life. An NRS ranging from 0 to 10 is used to answer the questions on the test.

The arithmetic mean of the 10 scales gives the BASFI score, which is a value between 0 and 10.

In case of missing answers to 1 or 2 of the single items within the BASFI questionnaire, the BASFI score will be calculated by imputing missing items with the mean of the completed items. Then, the BASFI score will be calculated as described above. If more than 2 of the items are missing, the BASFI score will be left missing.

#### Bath Ankylosing Spondylitis Disease Activity Index (BASDAI) 8.1.1.4

The BASDAI is the most commonly used instrument to . The BASDAI is a validated self-reported instrument which consists of 6 NRSs, each with 10 units to measure the severity of the 5 major symptoms:

over the last week. The BASDAI questionnaire is available in Section 12.7. To give each symptom equal weighting, the average of the 2 scores relating to is taken. The resulting 0 to 50 sum score is divided by 5 to give a final BASDAT score between 0 and 10, with lower scores indicating lower disease activity.

The BASDAI is calculated as follows:

$$BASDAI = \frac{Q1 + Q2 + Q3 + Q4 + (\frac{Q5 + Q6}{2})}{5}$$
(10)

where Q1 - Q6 are the six question from the BASDAI questionnaire.

If 1 of the 2

hisdoci

(ie, questions:

and

is missing, the other one will be used for the

morning stiffness calculation. The same imputation is also applied for the calculation of the ASAS inflammation component, which is calculated as the average of the 2 measurements.

If 1 major symptom of the BASDAI is missing, the sum score of the remaining symptoms will be divided by the number of symptoms assessed. If more than 1 major symptom is missing, the sum score will be set to missing.

#### 8.1.2 Primary analysis of the primary efficacy variable

The primary efficacy variable (ASAS40 at Week 12) will be analyzed for all subjects in the FAS.

itations thereof The dose-response relationship between treatment and ASAS40 response will be assessed with an ordered categorical analysis using a non-parametric correlation statistic of Mantel and Haenszel (Mantel and Haenszel, 1959) and modified ridit scores (Bross, 1958) with the corresponding p-value.

The analysis will include geographic region and prior TNF inhibitor exposure (yes/no) as stratification factors. Prior TNF inhibitor exposure will be used as stratification factor as it may have an impact on efficacy. The correlation between dose and ASAS40 response will be evaluated at a two-sided significance level of  $\alpha$ =0.05. This evaluation of dose-response will constitute the primary efficacy analysis.

A table will present the responder rates for placebo, BKZ 16mg, BKZ 64mg, BKZ 160mg, BKZ 320mg, and the correlation statistic of Mantel and Haenszel (ridit score) with the corresponding p-value.

NRI will be used to account for missing data; ie, subjects with a missing ASAS40 score at Week 12 or who discontinued study treatment prior to the Week 12 visit will be considered nonresponders for the primary analysis.

#### Secondary analyses of the primary efficacy variable 8.1.3

As the secondary analysis for the primary efficacy variable, a logistic regression model will be used to assess the effect of each individual dose versus placebo on ASAS40 response. The model will include fixed effects for treatment, geographic region, and prior TNF inhibitor exposure. To avoid the problem of the so-called monotone likelihood resulting in infinite large confidence intervals (eg, if one of the cell counts in the 2x2 table is equal to zero), a penalized maximum likelihood approach based on the modified score procedure of Firth (eg, Heinze and Schemper, 2002) will be used in the logistic models. If the logistic regression model is unable to converge, then a 2-way categorical variable for geographic region (North America and Europe) will be used. Should the logistic regression model be is unable to converge even with this restriction. then geographic region may be dropped from the model to facilitate convergence. If the logistic regression model be unable to converge after dropping the geographic region, then prior TNF inhibitor exposure may be dropped as well. Comparisons will be made for each dose versus placebo at a 2-sided significance level of  $\alpha$ =0.05. For each dose, the odds ratio versus placebo, the 95% confidence interval, and the corresponding p-value will be calculated. If the logistic regression model is unable to converge after dropping the geographic region, then prior TNF inhibitor exposure may be dropped as well. Comparisons will be made for each dose versus placebo at a 2-sided significance level of  $\alpha$ =0.05. For each dose, the odds ratio versus placebo, the 95% confidence interval, and the corresponding p-value will be calculated.

The pairwise comparisons of bimekizumab versus placebo will be formally evaluated for statistical significance only if the primary dose response efficacy analysis is statistically significant. Once the dose response has been established, pairwise testing of each bimekizumab dose versus placebo will account for multiplicity by using a fixed sequence testing procedure with each bimekizumab dose being tested sequentially from the highest dose to the lowest dose.

inis docu

If the dose-response relationship fails to reach significance at a significance level of  $\alpha$ =0.05, then the further pairwise comparisons are seen as non-significant.

A table will present the responder rates for placebo, BKZ 16mg, BKZ 64mg, BKZ 160mg, BKZ

NRI will be used to account for missing data; ie, subjects with a missing ASAS40 score at Week 12 or who discontinued study treatment prior to the Week 12 visit will be considered non-responders for the primary analysis. 8.1.4 -sk Isions or variati

#### 8.1.4 Supportive analyses of the primary efficacy variable

The following supportive analyses for the primary endpoint are planned:

- 1. The primary dose-response analysis and pairwise comparisons will be repeated for all subjects in the PPS to evaluate the effect of important protocol deviations on the analysis.
- 2. The primary dose response analysis and pairwise comparisons will be repeated for all subjects in the RS to evaluate the consistency of the FAS with the TT principle. Subjects with no valid measurement of the primary efficacy variable at Baseline will be included as non-responders. NRI will be used to account for missing data.
- 3. The change from Baseline in all ASAS components (ie, PGADA, total spinal pain, BASFI, and BASDAI) will be analyzed using the ANCOVA with treatment, geographic region, and prior TNF inhibitor exposure as fixed effects and the Baseline values as covariate. MI will be used for missing data (Section 4.2.1).

For the supportive analysis number 1 and 2 two tables will be displayed. One table will present the responder rates for placebo, BKZ 16mg, BKZ 64mg, BKZ 160mg, BKZ 320mg, and the correlation statistic of Mantel and Haenszel (ridit score) with the corresponding p-value. The other table will present the responder rates, and for each dose the odds ratios (differences to placebo), 95% confidence intervals, and corresponding p-values from the logistic regression.

For the supportive analysis number 3 tables will present the least-square means and standard error for placebo and bimekizumab dose for the ANCOVA models. For the pairwise comparison between placebo and bimekizumab dose the least-square means, standard error, corresponding pvalues, and 95% confidence intervals for the contrasts will be provided.

#### 8.1.5 Sensitivity analyses of the primary efficacy variable

Two sensitivity analyses will be performed for the primary dose response analysis and for the supportive analysis number 3:

1. This analysis evaluates the effectiveness of the treatment (de facto hypothesis) and will be This documen based on the ordered categorical analysis to evaluate dose-response as specified in the primary analysis. In an attempt to prevent missing data during the study, efforts will be made to collect data from subjects that withdraw early from the study. An analysis will be performed in which all available data at Week 12 will be considered. In this case, subjects will be analyzed according to their randomized treatment, even if they discontinued prior to Week 12 and were no longer on the randomized study treatment when the assessment was performed at Week 12. If Week 12 data for the ASAS response are not collected, the subject will be assumed to be a non-responder. It should be noted that this measures something

different from the primary analysis and could be confounded by placebo subjects who withdraw and are subsequently on another active medication at the time of the Week 12 assessment.

2. An additional sensitivity analysis will be based on observed data only for subjects who are still on the initially randomized treatment at Week 12. Subjects with missing data or who have prematurely discontinued study treatment will be excluded from the analysis. The same procedure described for the primary efficacy analysis of dose response will be used.

The following sensitivity analyses will be performed for the secondary analysis for the primary efficacy variable (pairwise comparison analysis of the primary efficacy variable) in order to assess the missing data assumptions:

- Missing data will be imputed using MI. In MI, the missing value is replaced by a set of
  plausible values, where each value is a Bayesian draw from the conditional distribution of the
  missing data given the observed data. Intermittent missing data will be imputed using the
  MCMC method, followed by monotone regression for monotone missing data to evaluate the
  effect of the method for handling missing data on the analysis. The ASAS components will
  be imputed individually and then the ASAS response will be calculated using the complete
  datasets. The multiply imputed data sets will be analyzed using a logistic regression model
  with fixed effects fixed effects for treatment, region, and prior TNF inhibitor exposure.
  Finally, the results will be combined into a single inference using Rubin's rule (Carpenter
  and Kenward, 2013). This procedure assumes a MAR pattern of missingness and corresponds
  to an estimand of what has been called the difference in outcome improvement if all subjects
  tolerated or adhered to treatment (Mallinekrodt et al, 2012). More details are available in
  Section 4.2.1.
- 2. The logistic regression model will be applied where all available data at Week 12 will be considered, as described in sensitivity analysis (1) for the primary efficacy variable.
- 3. The logistic regression model will be applied where only observed data for subjects still on the initially randomized treatment at Week 12 will be considered, as described in sensitivity analysis (2) for the primary efficacy variable.

The same tables as used for the primary and secondary efficacy analysis for the primary efficacy variable and for the supportive analysis number 3 with the different imputation analysis will be presented.

## 8.2 **Statistical analysis of the secondary efficacy variables**

The secondary efficacy variables will be analyzed for all subjects in the FAS.

All categorical variables (ie, ASAS20 response and ASAS5/6) will be analyzed for treatment effects using pairwise comparisons based on the same method as that for the primary efficacy variable.

All continuous variables (ie, ASDAS-CRP, BASDAI, and BASFI) will be analyzed for treatment effects using pairwise comparisons based on an ANCOVA model with treatment, geographic region, and prior TNF inhibitor exposure as fixed effects and the Baseline value as covariate.

thereof

For the categorical variables the responder rates for placebo, BKZ 16mg, BKZ 64mg, BKZ 160mg, BKZ 320mg, and for each dose the odds ratios (differences to placebo), 95% confidence intervals, and corresponding p-values from the logistic regression will be provided.

For the continuous variables the least-square means and standard error for placebo and bimekizumab dose for the ANCOVA models will be displayed. To pairwise compare placebo and bimekizumab dose the least-square means, standard error, corresponding p-values, and 95% confidence intervals for the contrasts will be provided. The ANCOVA model results for BASFF will be located in the supportive analysis section for the ASAS component and not in the secondary analysis section.

All categorical efficacy variables will be analyzed using observed cases as treated and imputed with NRI and all continuous variables will be analyzed using the MI.

## 8.2.1 Derivations of ASDAS-CRP, ASDAS-MI, and ASDAS Status

The ASDAS consists of a number of assessments which are scored by the subject and physician and multiplied by a proven formula (van der Heijde et al, 2009) as shown below:

- 0.121 x (BASDAI question 2 result)
- 0.058 x (BASDAI question 6 result)
- 0.110 x PGADA

, PGADA,

- 0.073 x (BASDAI question 3 result)
- 0.579 x (natural logarithm of the (hs-CRR [mg/L] + 1))

are all

assessed on a numerical scale (0 to 10 units) (Lukas et al, 2009).

The sum of these weighted components gives the ASDAS-CRP.

If one component for the ASDAS-CRP is missing at a given visit, that component will be imputed by carrying the last observation forward, and the ASDAS-CRP will be calculated accordingly. If no value is available for that component before the missing time point, the next observation may be carried backwards. If more than one component for the ASDAS-CRP is missing, ASDAS-CRP will be treated as missing.

If the hs-CRP value is below 2 mg/L, then it will be imputed as the constant value of 2 mg/L (Machado et al. 2015).

ASDAS Status in defined in four disease activity categories based on ASDAS-CRP as follows:

- Inactive Disease: ASDAS-CRP <1.3
- Moderate Disease Activity: ASDAS-CRP >=1.3 to <2.1
- ₩ High Disease Activity: ASDAS-CRP >=2.1 to <=3.5
- Very High Disease Activity: ASDAS-CRP >3.5

ASDAS-MI is defined as ASDAS-CRP reduction (improvement) of  $\geq 2.0$  relative to Baseline.

#### 8.3 Statistical analysis of other efficacy variables

Other efficacy variables will be analyzed for all subjects in the FAS, DBRS, ESS, cDBRS, cESS,

Times series plots will be provided for the provided for

and secondary efficacy variables. The plots will show the weekly response rate over the first 12 weeks.

The MRI of the spine and sacroiliac joints will be performed in a substudy with subjects who were classified as MRI-positive at Baseline as per ASAS-Outcome Measures in Rheumatology Clinical Trials (OMERACT) criteria.

A subset of the FAS will be used for the analyses of MASES. The MASES Score will only be analyzed for subjects with enthesitis at Baseline (MASES > 0)  $c^{2}$ 

Time to onset of ASAS20 response and ASAS40 response will be estimated and presented using the Kaplan-Meier product-limit method for each treatment. Time to a given response will be defined as the length in weeks from Baseline until the first date when the response is achieved. Following derivation will be used: Days from Baseline until the first date divided by 7. There will be no rounding for the Kaplan Meier estimates. Subjects who discontinue study prior to achieving a response will be censored at the date of study discontinuation. Subjects who reach the Week 12 visit without achieving a response will be censored at the date of the Week 12 visit. Missing response data will be imputed with NRI.

The median time to response including the 2-sided 95% confidence interval will be calculated for each treatment. Between groups differences (each bimekizumab dose versus placebo) will be analyzed using a log-rank test stratified by geographic region and prior TNF inhibitor exposure. Missing response data will be imputed with NRI.

Summary tables will be presented for the time to onset of ASAS20 response and ASAS40 response including following information: number of subjects achieving ASAS20/ASAS40 response, number of subjects censored, descriptive statistics (minimum, 25th percentile, median, 75th percentile, maximum) for the Kaplan-Meier estimates including the p-value (difference to placebo). Additional Kaplan-Meier Plots will be provided.

All other efficacy variables will be analyzed using observed cases as treated and imputed with NRI for binary variables and MI for continuous variables.

Subjects in the ESS who discontinue with bimekizumab treatment during the Dose-Blind Period will be treated as missing and categorical/continuous variables will be imputed.

In order to assess the potential bias of the potentially unblinded subjects based on data, the results of the final analysis will be utilized. Results of the ASAS40 response of the rerandomized 320mg and 160mg treatment group at Week 48 will be compared to the potentially unblinded, randomized 320mg and 160mg treatment groups. If the percentage of ASAS40 responders is

comparable as assessed by overlapping 95% confidence intervals, the potential bias is estimated to be at minimum.

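### Time to ASAS20/ASAS40 response: censoring Week 12 non-responders at their own unrounded visit date biases the Week 12 end of the Kaplan-Meier curve towards response

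*SAP*

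**What the plan says.** SAP Section 8.3 estimates time to onset of ASAS20 and ASAS40 response by "the Kaplan-Meier product-limit method for each treatment". The time scale is the actual date: "Following derivation will be used: Days from Baseline until the first date divided by 7", and "There will be no rounding for the Kaplan Meier estimates". The censoring rule for subjects still without response is "Subjects who reach the Week 12 visit without achieving a response will be censored at the date of the Week 12 visit". For those who leave early it is "Subjects who discontinue study prior to achieving a response will be censored at the date of study discontinuation", and the same paragraph adds "Missing response data will be imputed with NRI".

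The outputs are numerical as well as graphical: "The median time to response including the 2-sided 95% confidence interval will be calculated for each treatment". The summary table also carries the 25th and 75th percentiles and the numbers of responders and of censored subjects, and there are Kaplan-Meier plots. Each dose is compared with placebo by a stratified log-rank test.

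Section 2.2.1.3 schedules ASAS20 and ASAS40 at Weeks 1, 2, 4, 8 and 12 in the Double-Blind Period and lists both time-to-response variables among the other efficacy variables. Section 4.3.1 puts the same summaries and plots into the Week 12 interim analysis. The SAP has no rule that moves Week 12 assessments to a nominal time for this analysis.

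**The concern.** Kaplan-Meier treats a censored subject as someone who could still have the event later at the same rate as those left at risk. That is not the position of a Week 12 non-responder, who is censored because the last assessment that counts has been made and was negative.

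On unrounded dates, Week 12 events and Week 12 censorings do not tie. A non-responder seen on Day 82 has left the risk set when a responder seen on Day 86 is counted, so later Week 12 responses are divided by a shrinking denominator. Earlier visits do not have this problem, because non-responders there stay at risk.

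At stake are the end of the plotted curves and the tabulated median and 75th percentile. They would depend on how Week 12 visits happened to be scheduled. A table could show a median time to response beside a responder count below one half.

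**Working it through.** The SAP gives no figure for this analysis. Its one related statement, power above 99% for the trend test in Section 2.4, reproduces at 0.991 from the same planning inputs (57 per arm; ASAS40 rates of 40%, 36%, 20%, 15% and 12%; equally spaced scores; two-sided 0.05).

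**Assumptions.** The SAP gives neither the spread of Week 12 dates nor the share of responders whose first response is at Week 12. Both are varied below. The visit day is taken as independent of response.

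**Formula.** Let F be the true proportion responding at any visit up to Week 12, s the share of responders first responding at Week 12, F8 = F(1 − s), and h = Fs/(1 − F8). If Week 12 visits fall with equal probability on k days, then with m days left (m = k, …, 1) the hazard on that day is (h/k)/(m/k) = h/m. The large-sample Kaplan-Meier value at the end of the window is

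1 − (1 − F8) × (1 − h)(1 − h/2)…(1 − h/k).

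The true value is 1 − (1 − F8)(1 − h) = F. The cumulative hazard in the window is h(1 + 1/2 + … + 1/k) instead of h, which for k = 7 is 2.593h.

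**Numbers for F = 40%**

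- s = 25%: F8 = 0.30, h = 0.10/0.70 = 0.1429. For k = 3, 1 − 0.70 × 0.8571 × 0.9286 × 0.9524 = 46.9%.
- s = 10%: F8 = 0.36, h = 0.04/0.64 = 0.0625. For k = 3, 1 − 0.64 × 0.9375 × 0.9688 × 0.9792 = 43.1%.

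| Share first responding at Week 12 | No spread | ±1 day (k = 3) | ±3 days (k = 7) | ±7 days (k = 15) |
|---|---|---|---|---|
| 10% | 40.0% | 43.1% | 45.7% | 48.2% |
| 15% | 40.0% | 44.5% | 48.2% | 51.5% |
| 25% | 40.0% | 46.9% | 52.5% | 57.2% |

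Simulation with n = 57 per arm (5,000 runs) agrees; at a 25% share the means are 40.0%, 47.1%, 52.4% and 56.8%. Clustering the visits does not remove the bias: with half of them on Day 84 and the rest within ±3 days, the means are 49.6% (15% share) and 55.1% (25% share). At the other planning rates, with ±3 days and a 25% share, a true 36% gives 47.6%, 20% gives 27.2% and 12% gives 16.5%.

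**Median reported although fewer than half responded (true 40%, n = 57).** For shares of 15% to 25% this happens in 0% of runs with no spread, 18–30% at ±1 day, 33–50% at ±3 days and 40–58% at ±7 days. A separate simulation (3,000 trials) over shares of 10% to 25% gave 12–28% at ±1 day and 23–51% at ±3 days. The planning rates are response at Week 12. The proportion who responded at any visit by then is at least as high, which puts the 36% and 40% arms nearer one half.

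**Nominal weeks.** Week 12 events and censorings then tie, and events are counted first. The simulated curve equals the crude proportion (40.0% for a true 40%; 44.7% for both in the run with a true 45%), and no median is reported with fewer than half responding.

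**The case against.** The mechanism is hard to dispute, but several limits on it stand.

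- **Standing of the variable.** This is an other efficacy variable. The primary Mantel-Haenszel analysis, the pairwise logistic regressions, the secondary variables and the fixed-sequence testing do not use the curve.
- **Treatment comparison.** A reader might infer that the log-rank comparisons are also misleading. The evidence does not support this. In an unstratified simulation (57 per arm, 25% of first responses at Week 12, 2,000 runs per setting), size at an equal 25% response was 0.047, 0.038, 0.045 and 0.049 for spreads of 0, ±1, ±3 and ±7 days. Power at 44% against 18% was 0.87, 0.86, 0.85 and 0.84. The planned test is stratified and was not simulated, but there was no sign of inflation.
- **Size.** The bias depends heavily on the share of first responses at Week 12. For a true 44% the curve ends at 51%, 57% and 62% (±1, ±3, ±7 days) with a 25% share, but at 46%, 47% and 49% with a 5% share. No single figure should be quoted as the effect.
- **Mismatch with Week 12 responder rates.** A reader might expect the curve to equal the Week 12 NRI responder rate. It need not: the curve concerns response at any visit by Week 12, and the two differ even when the curve is correct.
- **Visible counts.** The table shows the numbers responding and censored, so a careful reader can compare the crude proportion with the median. This helps, but it leaves the percentile and the plot wrong.
- **Dropouts.** A reader might see a contradiction between censoring at study discontinuation and NRI. NRI can settle response status at a missed visit while the censoring rule sets follow-up time, so this is an arguable choice of estimand and not part of the main error. With nominal weeks and an assumed 10% dropout, Kaplan-Meier gives 39.9% against a crude 38.0%.

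**Conclusion.** The point holds for the Week 12 segment of the Kaplan-Meier curves and for any percentile that falls there, chiefly the median and the 75th percentile. Two rules cause it together: unrounded dates, and censoring at the subject's own Week 12 date. The bias is towards more response whenever Week 12 dates differ and some first responses occur at Week 12; it vanishes only if one of these conditions fails. For a true 40% and shares of 10% to 25%, it is about 3 to 7 percentage points at ±1 day, 6 to 13 at ±3 days and 8 to 17 at ±7 days. Both the share and the spread are assumptions.

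This should be fixed, because the rule as written can report a median that the data do not support, and the same output appears in the Week 12 interim. It does not call the trial's primary or secondary conclusions into question.

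**What to change.** In SAP Section 8.3, do one of the following:

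- Use the nominal visit week (1, 2, 4, 8, 12) as the time scale for the Kaplan-Meier estimate and, for consistency, for the log-rank test.
- Keep actual dates for responses, but censor every subject who reaches Week 12 without response at one common time, tied with or after the last Week 12 response.

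If no one is censored before Week 12, either rule makes the curve at Week 12 equal the crude proportion who responded at any visit. The second rule was not simulated; it follows because no non-responder then leaves before the last event.

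Separately, add a sentence saying how censoring at study discontinuation fits with NRI in the same paragraph: either dropouts are censored when they leave, or they are carried to Week 12 as non-responders.

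The cost is SAP wording and a re-run of the ASAS20 and ASAS40 time-to-response tables and plots, with no new data. If the interim used the present rule, the difference belongs in Section 4.3.1.1, which already records such changes. The displayed response will be less favourable where Week 12 dates were spread.
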